8.3. Diary8.3.1. Diary for transplanted patient (Group A)

8.3.2.	Diary for NON-Tran	planted patient	(Group B)
--------	---------------------------	-----------------	-----------

Time from registration	D0 Screening	D30 M1	D60 M2	D90 M3	D120 M4	D150 M5	D180 M6	D240 D365 M8- M12	D365 D990 M12-M33	D1080 M36
Inform consent	х									
Clinical visit	x	X2/ M	x	х	x	x	x	X Every 2 months	X Every 3 months	x
Comorbidity assessment	x			x						
ECOG	х	х	х	х	х	х	х	х	х	х
Blood cell counts (9)	x	X1/ W	X1/M	X1/M	X1/M	X1/M	X1/M	X1/M	X1/M	X1/M
Standard biology (1)	х	х	х	х	х	х	х	х	х	х
EPO, folates, B12	х									
Iron plasmatic dosage (2)	x	x	x	x	x	x	x	x	x	x
HLA typing (3)	х	х	х							
Centralized biological study (4)	Х*			x					M16	
Proteinuria	х	х	х	х	х	х	х	х	х	х
Bone marrow aspiration + blood + cytogenetics (5)	x								M12 &24	x
Heart and liver MRI (6)	x			x						
QOL	x								M12 & 24	x
AE Grade III-IV	x	x	х	х	x	x	x	x	x	х

(1) Every visit: Proteinuria, AST, ALT, serum bilirubin, serum creatinine, PAL, LDH, GGT, CRP

(2) Serum ferritin, transferrin, iron plasmatic level

(3) HLA A, B, C, DRB1 molecular level

(4) Centralized study – 2 tubes without EDTA 5 mL to Louis Mourier Hospital, see specificity in appendix 10. *Before Exjade initiation (5) Inclusion, D60 to D100 post-transplant or once a year for non-transplant patient. Including cytogenetic and centralized shipment

for molecular analysis to CHRU Lille (BM 2 ml EDTA + Blood 2 tubes 5 mL with EDTA)

(6) Only for patients with SF > 1000 ng/mL or more than 20 RBC transfusions at time of inclusion. At time of screening, could be done within 6 weeks before or after inclusion. *After transplant, should be done at D100 and before Exjade restarting

(7) Include cardiac and pulmonary assessment

(8) Assessment at D30. *Should be repeated at the next visits only if the first one is not donor > 95% or in cases a rejection is suspected

(9) Including reticulocytes and blast count

9. Statistical analysis

9.1. Sample size

The objective of this study is to demonstrate an improvement of the overall survival in patients with a donor that is reaching 70% at 36 months compared to 40% in those without a donor. To test this hypothesis (HR=0.39) based on a two-sided log-rank test, 50 events are required, and 105 patients are needed with a 80% power and type I error rate at 5%, with a probability to identify a donor at 70%.

9.2. Duration of the study

The study is based on a cohort of patients prospectively enrolled. The main criterion is a right-censored end point that will be compared across groups of patients either transplanted or not, on the basis of a log-rank test. It has been computed that 50 events are required to control for the type I and II error rates, with an estimated sample size of 105 patients. Thus, according to the expected recruitment rate and survival rate, it is supposed that the study will end up 5 years after the trial onset, that is, between 2 and 5 years after patient accrual.

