3.1 Primary Objective

The primary objective of the study is to compare overall survival in patients with or without a matched donor (8/8 unrelated donor or matched sibling) at 36 months.

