6.1. Group A: Patients with a donor

- Iron chelation

Patients with iron overload defined as more than 20 blood cell transfusions (since initial diagnosis) or ferritin level > 1000 ng/mL will start Exjade® at 20 mg/kg per day of deferasirox dispersible tablets or 14 mg/kg per day of deferasirox film-coated tablets (when converting a patient from deferasirox dispersible tablets to deferasirox film-coated tablets, the dosage should be decreased by 30%) or will continue Exjade® if they were receiving it before inclusion at a minimal dosage of 20 mg/kg of deferasirox dispersible tablets or 14 mg/kg of deferasirox film-coated tablets or same dose if they were receiving a higher dose. Exjade® will be temporarily discontinued one day before conditioning regimen start or at any moment in case of renal failure (clearance < 60 ml/min). In those patients, Exjade® will be restarted on day 100 in patients with LIC > 5 mg Fe/gr dry weight (defined before the transplantation), except in cases of contraindications including gastro-intestinal disorder (nausea, vomiting, abdominal pain or diarrhea), renal failure (clearance < 60 ml/min), active GVHD, neutropenia < 0.5 G/L, thrombocytopenia < 30 G/L, total bilirubin, AST, ALT > 2xULN, GGT and PAL > 3xULN.

Before restarting Exjade[®], complete iron measurements will be repeated (serum iron, serum ferritin, transferrin saturation, NTBI, LPI, hepcidine) and MRI.

The initial dose of Exjade[®] after transplant will be 10 mg/kg/day of deferasirox dispersible tablets or 7 mg/kg per day of deferasirox film-coated tablets progressively increased to 20 mg/kg/day or 14 mg/kg/day respectively if good tolerance.

Patients with iron overload will be evaluated at each visit by serum ferritin, transferrin and iron in serum; will be evaluated 12 months after transplant by complete iron measurements including serum iron, serum ferritin, transferrin saturation, NTBI, LPI and hepcidine.

Hepcidine and non-transferrin binding iron will be measured in the ancillary biological study (Hôpital Louis Mourier, see appendix 10).

As soon as ferritin reached a level < 700 ng/mL, Exjade[®] will be discontinued.

- Transplantation (D0)

The HSCT should be **scheduled 4 months after the inclusion** either with an HLA-matched sibling or a 8/8 (A,B,C,DRB1) HLA matched unrelated donor.

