9.3. Statistical analysis

All analyses will be performed in an intent-to-treat approach, whatever the treatment actually performed (either transplantation or not); the basis for comparison will indeed be the selection of a donor or not. Such a design is often considered as a "Mendelian randomization". Mendelian randomization is a method that allows one to test for, or in certain cases to estimate, a causal effect from observational data in the presence of confounding factors⁹⁰. From a statistical perspective, it is an application of the technique of instrumental variables⁹¹, with genotype acting as an instrument for the exposure of interest. However, Mendelian randomization estimates are especially relevant when the effect of interest is that of a long term population based intervention. Otherwise, a Mendelian randomization approach will generally be qualitatively informative for the direction of effect of a clinical intervention, the genetically derived estimate might not correspond to the magnitude of the effect in practice. Thus, two analyses will be conducted, with two main estimates of intervention effect:

- directly comparing those two groups (donor vs no donor)
- using inverse probability treatment weights, based on the propensity scores to have actually a donor.

Baseline characteristics, overall and complete response rates of the two groups will be compared by nonparametric tests, either the exact Fisher's exact test for qualitative variables or the Mann-Whitney test for quantitative variables. Cumulative incidences of AML will be tested with the Gray test considered death as a competitive event. Prognostic factors of event-free and overall survival will be investigated using Cox proportional hazard models. Model assumptions will be checked using a test for proportional hazards and spline smoothing of residuals for the log-linearity assumption.

All statistical analyses will be performed with the R and SAS software packages.

10. Safety assessment

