Appendix 11. Study procedures

GROUPE A: Transplanted patients

Time from HSCT	Screening D-120 M-4	D-90 M-3	D-60 M-2	D-30 M-1	D0 HSCT	D30 M1	D60 M2	D120 D240 M4-M8	D240 D930 M8-31	D480 M16
Inform consent	х									
Clinical visit	x	X2/ M	x	x	x	х	х	X Every 2 months	X Every 3 months	x
Comorbidity assessment	x			х						
ECOG	х	х	х	х	х	х	х	х	х	х
Blood cell counts (9)	x	X1/ W	X1/M	X1/M	X1/M	X1/M	X1/M	X1/M	X1/M	X1/M
Standard biology (1)	х	x	х	х	х	х	х	х	х	x
EPO, folates, B12	х									
Iron plasmatic dosage (2)	x	x	x	x	x	х	x	х	x	x
HLA typing (3)	х	X	х							
Centralized biological study (4)	Х*			D-5 Pre- Allo	D0 before HSCT	D7 and D30 post allo		D 100 post Allo		M12 post- Allo
Proteinuria	х	х	х	х	х	х	х	х	х	х
Bone marrow aspiration + blood + cytogenetics (5)	x							D100 post Allo	M12, 24 &36 post inclusion	
Heart and liver MRI (6)	x			x				Х*		M12 post allo
QOL	x								M12, 24 &36 post inclusion	
AE Grade III-IV	х	x	х	х	х	x	х	х	х	x
Pregraft tests (7)			х							
GVHD assessment						х	Х	х	Х	X
Postgraft blood chimerism (8)						х	Х*	Х*	Х*	
Confirming date of HSCT		x	х	x						

GROUPE B: NON-Transplanted patients

Time from registration	D0 Screening	D30 M1	D60 M2	D90 M3	D120 M4	D150 M5	D180 M6	D240 D365 M8- M12	D365 D990 M12-M33	D1080 M36
Inform consent	х									
Clinical visit	x	X2/ M	x	x	x	x	x	X Every 2 months	X Every 3 months	х
Comorbidity assessment	x			x						
ECOG	х	х	х	х	х	х	х	х	х	х
Blood cell counts (9)	x	X1/ W	X1/M	X1/M	X1/M	X1/M	X1/M	X1/M	X1/M	X1/M
Standard biology (1)	х	х	х	х	х	х	х	х	х	х
EPO, folates, B12	х									
Iron plasmatic dosage (2)	x	x	x	x	x	x	x	х	x	х
HLA typing (3)	х	х	х							
Centralized biological study (4)	X*			x					M16	
Proteinuria	х	х	х	х	х	х	х	х	х	х
Bone marrow aspiration + blood + cytogenetics (5)	x								M12 &24	х
Heart and liver MRI (6)	x			х						
QOL	x								M12 & 24	х
AE Grade III-IV	х	х	х	х	х	x	х	х	x	х

(1) Every visit: Proteinuria, AST, ALT, serum bilirubin, serum creatinine, PAL, LDH, GGT, CRP

(2) Serum ferritin, transferrin, iron plasmatic level

(3) HLA A, B, C, DRB1 molecular level

(4) Centralized study – 2 tubes without EDTA 5 mL to Louis Mourier Hospital, see specificity in appendix 10. *Before Exjade initiation

(5) Inclusion, D60 to D100 post-transplant or once a year for non-transplant patient. Including cytogenetic and centralized shipment for molecular analysis to CHRU Lille (BM 2 ml EDTA + Blood 2 tubes 5 mL with EDTA)

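### Section 9.2 groups the primary survival comparison by transplant received, contradicting the donor versus no-donor basis used everywhere else; if followed from inclusion, it would build in immortal time

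*Protocol*

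**What the plan says.** Section 9.2 (Duration of the study) says the main criterion, a right-censored endpoint, will be "compared across groups of patients either transplanted or not, on the basis of a log-rank test". It gives no time origin, no landmark and no time-dependent handling of transplantation.

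The rest of the protocol groups by donor:

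- Section 3.1: the objective is to "compare overall survival in patients with or without a matched donor (8/8 unrelated donor or matched sibling) at 36 months".
- Section 9.1, repeated in the synopsis: survival in donor patients "reaching 70% at 36 months compared to 40% in those without a donor", followed by "To test this hypothesis (HR=0.39) based on a two-sided log-rank test, 50 events are required".
- Section 9.3: analyses are intent-to-treat whichever treatment was carried out, and "the basis for comparison will indeed be the selection of a donor or not".

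Four other provisions bear on the difference between the groupings:

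- Section 6.1 has the transplant "scheduled 4 months after the inclusion".
- Section 3.2 expects 80-95% of donor patients to be transplanted.
- Sections 6.1 and 6.2 allow an alternative-donor transplant on progression, in Group B and in Group A patients not transplanted as planned.
- Section 6 assigns patients to Group A or B at least 2 months after inclusion.

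**The concern.** Transplanted and having a donor are not the same thing in this trial. Some donor patients will not be transplanted, and some patients without a matched donor may be. Section 9.2 therefore defines a different primary analysis from 9.3, using the variable that 9.3 says to disregard.

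The difference is not neutral. With time counted from inclusion, nobody in the transplanted group can die before the transplant date, while every earlier death, including those of donor patients, falls in the comparator. This immortal time favours transplantation even if it has no effect. It also discards the donor-based protection against confounding that 9.3 gives as the reason for the design.

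**Working it through.** **The plan's own figure.** HR = ln(0.70)/ln(0.40) = 0.357/0.916 = 0.389, which matches the stated 0.39. So 9.1 powers a log-rank test on donor versus no donor. (Schoenfeld's formula at 80% power gives 37 events at 62:43 and 42-43 at 70:30, not 50. That is a separate matter and does not affect this point.)

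**Inputs from the protocol.**
- N = 105; two-sided log-rank test at 5% (9.1)
- Donor share: 70% (9.1), or 62/105 = 59% (section 5)
- 80-95% of donor patients transplanted (3.2); transplant at month 4 (6.1)
- Accrual over 36 months, end at month 60, so 24-60 months of follow-up (synopsis)

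**Assumptions.** No effect of donor or transplant; exponential survival; uniform accrual; time zero at inclusion. A patient is transplanted if he or she has a donor, is alive at month 4 and proceeds. The 80-95% is applied to donor patients alive at month 4. Alternative-donor transplants are not modelled.

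**How patients move between groups** (40% survival at 36 months, 70% donor, 95% transplanted).
- Alive at month 4: 0.40^(4/36) = 0.903
- Donor patients: 0.70 × 105 = 73.5
- Transplanted: 73.5 × 0.903 × 0.95 = 63.1
- Donor patients dead before month 4, moved to the comparator: 73.5 × 0.097 = 7.1
- All deaths before month 4: 105 × 0.097 = 10.2, every one in a comparator of about 42 patients and none in the transplanted group

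**Simulated rate of a false significant benefit under the 9.2 grouping** (nominal 2.5%; 5,000-20,000 runs per setting).

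| Survival at 36 months, all patients | 59% donor, 80% transplanted | 70% donor, 95% transplanted |
|---|---|---|
| 40% | 19-20% (median HR 0.76) | 39% (median HR 0.66) |
| 61% | 11% | 22% |
| 70% | 9% (median HR 0.81) | 17% (median HR 0.72) |

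The 61% row is the planned mix: 0.70 × 0.70 + 0.30 × 0.40 = 0.61. At 40% survival, a delay of 2 months would give 9-15% and a delay of 6 months 35-64%.

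**Alternatives in the same simulation, 40% survival.**
- Donor versus no donor, status fixed regardless of early death: two-sided error 5.1-5.4%, false benefit 2.8-3.2%
- Transplanted versus not, landmark at month 4: two-sided error 5.3-5.4%
- Donor versus no donor, but deaths before a 2-month assignment counted as no donor (an assumption): false benefit 12-17%

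**The case against.** The strongest reply is that the document already settles the matter. Section 9.3 is the governing analysis section, covers all analyses and expressly sets aside the treatment carried out. Sections 3.1 and 9.1 and the synopsis agree with it. The outlier is one clause in a paragraph about when 50 events will have accrued. A statistician following 9.3 would not run the 9.2 grouping. This stands as to likely intent: the clause is probably a drafting slip.

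It does not remove the need for a correction. Section 9.2 is an explicit statement of groups and test for the main criterion, and 9.3 names no test for the survival comparison.

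Three stronger readings are tempting, and the documents do not support them:

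- A reader might infer that 9.2 alone ties the main criterion to its test and therefore governs. Section 9.1 ties overall survival by donor status to a two-sided log-rank test.
- A reader might take the schedule headings, "Diary for transplanted patient (Group A" and "GROUPE B: NON-Transplanted patients", as further evidence of an analysis by transplant received. They are visit schedules. The Group A schedule counts time from transplant and includes graft and GVHD assessments, so it fits transplanted patients and could not serve the 5-20% of donor patients expected not to be transplanted.
- A reader might take the upper simulated rates as what this trial will produce. They apply only if 9.2 is followed, and from inclusion.

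**Conclusion.** The point holds as a contradiction on the primary comparison, wrong as written in 9.2 and contradicted by the rest of the protocol. If 9.2 were followed, the bias would favour transplantation. Over the settings examined at the scheduled 4 months, false benefit runs from about 9% to 39%, against 2.5%. Where it falls depends mainly on overall survival, the donor share and the share transplanted.

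The size rests on time running from inclusion and on a constant hazard. Alternative-donor transplants, if counted as transplanted from inclusion, would add further immortal time.

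The donor grouping is itself protected only if donor status does not depend on surviving the search. The protocol assigns groups at least 2 months after inclusion. It does not say that earlier deaths count as no donor, so the 12-17% shows what should be ruled out and is not a fault found in the plan.

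**What to change.** - In 9.2, replace the reference to groups transplanted or not with: *patients with or without a matched donor (Group A vs Group B), whatever treatment is received*.
- State the time origin for overall survival in the same place.
- State that donor status does not depend on surviving the search, so that deaths before assignment are not counted as no donor by default.
- If a transplanted-versus-not analysis is wanted, make it secondary, with transplantation as a time-dependent covariate or with a landmark.
- Leave the transplant-anchored schedules in 8.3 and Appendix 11 labelled as for transplanted patients.

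The cost is a wording amendment, with no new patients or data.

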9.3. Statistical analysis

All analyses will be performed in an intent-to-treat approach, whatever the treatment actually performed (either transplantation or not); the basis for comparison will indeed be the selection of a donor or not. Such a design is often considered as a "Mendelian randomization". Mendelian randomization is a method that allows one to test for, or in certain cases to estimate, a causal effect from observational data in the presence of confounding factors⁹⁰. From a statistical perspective, it is an application of the technique of instrumental variables⁹¹, with genotype acting as an instrument for the exposure of interest. However, Mendelian randomization estimates are especially relevant when the effect of interest is that of a long term population based intervention. Otherwise, a Mendelian randomization approach will generally be qualitatively informative for the direction of effect of a clinical intervention, the genetically derived estimate might not correspond to the magnitude of the effect in practice. Thus, two analyses will be conducted, with two main estimates of intervention effect:

- directly comparing those two groups (donor vs no donor)
- using inverse probability treatment weights, based on the propensity scores to have actually a donor.

Baseline characteristics, overall and complete response rates of the two groups will be compared by nonparametric tests, either the exact Fisher's exact test for qualitative variables or the Mann-Whitney test for quantitative variables. Cumulative incidences of AML will be tested with the Gray test considered death as a competitive event. Prognostic factors of event-free and overall survival will be investigated using Cox proportional hazard models. Model assumptions will be checked using a test for proportional hazards and spline smoothing of residuals for the log-linearity assumption.

All statistical analyses will be performed with the R and SAS software packages.

10. Safety assessment

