1.2. Poor prognostic features in the lower risk MDS patients

Several evidences have shown that the lower risk patient group is a heterogeneous group and some of these patients will have a poorer outcome than expected according to their IPSS. The MD Anderson Cancer Centre (MDACC) team has developed a clinical and biological score taking into account age in the lower risk MDS patients age (> 60 years), haemoglobin (10 g/dL), platelet count (50 G/L) and marrow blast count (> 3%). This "MDACC" score is able to discriminate 3 groups inside the lower risk with median survival as follow: 5.9, 2.65 and 1.11 years¹³. Furthermore, the IPSS has been recently revised giving 5 categories (instead of 4) which differ slightly with the previous score giving a higher score to 25% of the lower risk according to classical IPSS. This quarter of patients are generally categorized in the "intermediate" risk with a median life expectancy at 3

years¹⁴. Another poor prognostic factor in the low risk patients is the failure ESA. Kelaidi et al have reported a worsened overall survival in low risk patients refractory or with an early relapse after erythropoiesis-stimulating agents¹⁵ and it has been also confirmed by others⁵. Molecular analyses have recently emerged as potential prognostic markers. Indeed, some somatic mutations can have an adverse impact on outcome, particularly for the lower risk patients. Acquired mutations have been detected in several genes and most frequent mutations (> 5%) have been reported in SF3B1, TET2, RUNX1, ASXL1, SRSF2, TP53, U2AF1, NRAS/KRAS, DNMT3A, ZRSR2, EZH2, less frequently in CBL, IDH2, KRAS, NPM1, NRAS, RUNX1, NPM1, ETV6, SF1, SETBP1, SF3A1, U2AF65, PRPF40B^{13,16-19}. Most of these mutated genes are not specific but have been reported present in 50 to 70% of patients with normal cytogenetic. More specifically, lower risk del 5q MDS patients with TP53 mutations appear resistant to lenalidomide and have a higher risk of AML occurrence. TP53 mutations in low-risk myelodysplastic syndromes with del 5q predict disease progression²⁰⁻²² while Bejar et al did not retain TP53 mutation as a poor prognostic factors in his low risk MDS cohort¹³. The screening of such somatic mutations is not routinely done yet but still remains under prospective and retrospective investigations before engaging molecular based treatment strategies.

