Transplant procedure influences also outcome. The advent of reduced intensity conditioning (RIC) regimen has decrease NRM allowing transplantation in older patients (representing the majority of patients with MDS) or with some comorbidities^{70,71,72}. In fact, all retrospective studies comparing RIC versus MAC regimen reported similar overall survival because a lower NRM is counterbalanced by a higher relapse rate^{73,58,74} and a prospective randomized study in MDS patients has same conclusions (not published yet, presented at ASH 2014, San Francisco, Abstract 320, Kroger et al). In disease in remission, there are few evidences to do MAC in patients older than 50 years while active disease with high blast count are less controlled with HSCT preceded by a RIC⁷⁵. Concerning the source of stem cells, HLA-identical sibling and HLA-identical unrelated donor are the preferred source, given similar results while alternative source of stem cells (HLA mismatched unrelated or unrelated cord blood) seem given worse results in registries studies^{76,77}.

Finally, Della Porta study perfectly resumes potential risk factors for outcome in their multivariate analysis: age (> 50 years); IPSS-R; comorbidity index; monosomal karyotype; type of donor (sibling versus matched unrelated)⁶⁵.

Anti-T Lymphocyte (ATG) in the transplant setting

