In all retrospective studies, the proportion of low risk patients is around 20% indicating that transplant decision has been taken in a substantial proportion of patients. As reported above, survival after transplantation is better in these low risk patients ranging from 50 to 94% according to other potential prognostic factors^{60,68,65}. On the other hand, as detailed in the previous section, these lower risk patients have not always prolonged survival as estimated by classical IPSS because other parameters potentially have an impact on their survival. Among these prognostics factors: there are no response to treatment, poor cytogenetic, profound cytopenia requiring regular transfusion, iron overload and some somatic mutations. This is not really known today if all these prognostic factors overlap but some correlation between biology¹⁶ and somatic mutations or between response to treatment and somatic mutations²⁰⁻²² have been reported. With one or several of these risk factors, low risk patients have an expected median survival lower than 3 years while post-transplant outcome is expected > 3 years in this category of patients. The aim of the present phase II study is to analyse outcome of the low risk patients with poor prognostic feature with or without a transplant according to donor availability.

2. Type of Study

This is a controlled, non-randomized multicenter, phase II study.

3. Study Objectives

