8.1. At inclusion

After checking the inclusion and exclusion criteria, as well as parameters necessary for stratification, the investigator will request inclusion online.

The following information will be collected:

- Medical history: date of diagnosis and initial disease characteristics (blood counts, bone marrow results, cytogenetic analysis)
- Previous treatments and history of RBC and platelet transfusions

Then, the investigator will:

- Check inclusion criteria
- For young patients, 18-45 years, contact [name] by e-mail ([contact])

- Collect the informed consent (clinical +/- biological study)
- Perform clinical examination: weight, height, PS (ECOG, Appendix 1), co-morbidity (Appendix 2-3)
- Perform baseline blood tests including: full blood count and differential, including peripheral blasts count and reticulocytes, AST, ALT, serum bilirubin, LDH, PAL, GGT, creatinine, EPO level, CRP, B12 and folates test
- Urine test: proteinuria
- Perform bone marrow aspiration for morphology, cytogenetics, and correlative biological studies (2 mL EDTA). If this analysis has been done within the 2 months prior to inclusion and if peripheral blood cell counts are stable: a new bone marrow aspiration could be avoided if BM sample have been sent to the CHRU of Lille, [name] laboratory, and SMD molecular analysis have already been performed (ASXL1, TP53, EZH2, ETV6, RUNX1...)
- Send bone marrow (2 ml EDTA) and blood (10 ml EDTA) samples for molecular analysis
- Send serum, 10 ml (2 tubes 5 ml without EDTA or citrate), before Exjade[®] initiation, to Louis Mourier Hospital for iron biological study
- HLA will be performed in these patients and in their siblings (if available and age < 70 years without cancer, thrombosis or cardiac failure history). If no donor is available among siblings, a matched unrelated donor 8/8 unrelated donor is searched. Antibodies against HLA should also be checked.
- Iron overload will be estimated at registration by the number of transfusions received since initial diagnosis, iron parameters (serum iron, transferrin saturation, serum ferritin)
- **Heart and liver MRI** should be performed within 6 weeks in patients with iron chelation criteria: ferritin level > 1000 ng/mL (can be done also before inclusion, maximally 6 weeks before)
- Pregnancy test, if applicable
- Quality of life questionnaire (EORTC)

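### The direct donor versus no-donor survival comparison names no covariate or stratum, and section 9.3 does not say whether it or the propensity-weighted analysis decides

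*Protocol*

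**What the plan says.** Section 2 describes the design: "This is a controlled, non-randomized multicenter, phase II study". Section 9.1 sizes it: "based on a two-sided log-rank test, 50 events are required", for 36-month survival of 70% with a donor and 40% without. Section 9.2 repeats the test: "The main criterion is a right-censored end point that will be compared across groups of patients either transplanted or not, on the basis of a" (the sentence closes by naming the log-rank). (Section 9.2 describes the groups by transplantation; I follow sections 9.1 and 9.3, which compare by donor.)

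Section 9.3 lists two main estimates of the intervention effect. One is "directly comparing those two groups (donor vs no donor"). The other uses inverse probability weights from a propensity score for having a donor. Neither is given precedence. Cox models are planned for prognostic factors, but the text does not say that they adjust the donor effect.

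On prognosis, section 1.2 cites a score built on age, haemoglobin, platelets and marrow blasts that can "discriminate 3 groups inside the lower risk with median survival as follow: 5.9, 2.65 and 1.11 years". Section 1.4 cites a multivariate analysis of transplanted patients that found "age (> 50 years); IPSS-R; comorbidity index; monosomal karyotype; type of donor (sibling versus matched unrelated"). Age and IPSS-R enter eligibility (4.1), and comorbidity is recorded at inclusion (8.1, Appendix 3). Section 8.1 also has the investigator check eligibility "as well as parameters necessary for stratification", but section 9 uses no stratification.

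**The concern.** Without randomisation, nothing guarantees that the donor and no-donor groups have the same prognosis at inclusion. A log-rank test without strata reads any prognostic difference as a donor effect. Even with balanced groups, it gives up power that a test using strong baseline factors would recover. The factors are known and already collected, so adjusting costs no data.

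The weighted analysis answers the first problem. But because the two main estimates are not ranked, a positive plain log-rank could be reported as the trial's result even if the weighted estimate disagreed.

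**Working it through.** **Inputs from the protocol.** 105 patients; accrual 36 months, end at month 60, so 24 to 60 months of follow-up each; two-sided 5%; 36-month survival 70% versus 40%; donor share 70% (9.1) or 62/105 = 59% (section 5).

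**The plan's own figures.** HR = ln 0.70 / ln 0.40 = 0.389, which reproduces 0.39. Schoenfeld events = (1.96 + 0.842)² / [p(1−p)(ln HR)²]:
- p = 0.70: 7.85 / (0.21 × 0.890) = 42 (43 with HR rounded to 0.39)
- p = 0.59: 7.85 / (0.242 × 0.890) = 36.5, so 37

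The stated 50 events is not reproduced from these inputs, but it errs on the safe side. Power at 50 events = Φ(√(50·p(1−p))·|ln HR| − 1.96) = 86% (p = 0.70) or 91% (p = 0.59). Expected deaths by month 60 under exponential survival are 33.7% of donors and 64.5% of the others: 73.5 × 0.337 + 31.5 × 0.645 ≈ 45 at 70:30, and 62 × 0.337 + 43 × 0.645 ≈ 49 at 62:43.

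**Assumptions not in the documents.** Model A: a continuous prognostic score with HR per SD of 1.5 or 2.0, and donors better by 0, 0.2 or 0.4 SD (2,000 trials per cell). Model B: three strata with the section 1.2 medians, rescaled to 40% no-donor survival at 36 months, with assumed shares (10,000 trials per scenario).

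The models can be put on one scale. Log hazards in B are −ln 5.9, −ln 2.65 and −ln 1.11. With shares 20/50/30 their SD is 0.587, an HR per SD of e^0.587 = 1.8. Equal shares give 2.0, and 5/60/35 (few patients in the best group) gives 1.6. Moving 10 points from the worst to the best stratum at 20/50/30 is 0.10 × ln(5.9/1.11) / 0.587 = 0.28 SD; 20 points is 0.57 SD.

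**Power at 70% versus 40%, no imbalance (model A).**

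| Donor share | HR per SD | Log-rank | Weighted Cox | Adjusted Cox |
|---|---|---|---|---|
| 59% | 1.5 | 89.7% | 90.1% | 92.2% |
| 59% | 2.0 | 91.1% | 92.8% | 95.8% |
| 70% | 1.5 | 86.8% | 87.0% | 89.0% |
| 70% | 2.0 | 85.9% | 87.7% | 93.1% |

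Adjustment adds 2 points for the moderate score and 5 to 7 for the strong one; weighting adds 0 to 2. Model B gives 87–91% rising to 90–96%, a gain of 2 to 6 points; a repeat run gave 87–92% and 91–96%.

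**Two-sided rejection with no donor effect.**

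| Imbalance favouring donors | Log-rank | Weighted | Adjusted or stratified |
|---|---|---|---|
| 0.2 SD, HR per SD 1.5 | 4–6% | 3–4% | 4% |
| 0.2 SD, HR per SD 2.0 | 7–8% | 3% | 5% |
| 0.4 SD, HR per SD 1.5 | 10% | 4–5% | 5% |
| 0.4 SD, HR per SD 2.0 | 15% | 2–3% | 5–6% |
| Model B, 10 points worst to best | 10% | 3% | 5% |
| Model B, 20 points worst to best | 22–24% | 3% | 5% |

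In the 5/60/35 mix, moving 10 or 20 points from the worst to the middle stratum gives 7.5% or 11% for the log-rank.

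**Weighting versus adjustment when imbalance is real.** At 0.4 SD with the true effect present, adjusted Cox power exceeds weighted power by 3.2 points (90.2 v 87.0) to 8.8 points (92.0 v 83.2). Both stay above 80%. The weighted test rejects only 2 to 5% under the null, so it is conservative here, and part of its shortfall may come from the robust variance used.

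**The case against.** The strongest reply is that imbalance is already handled, by an analysis that the protocol calls main. That stands. A reader might infer from the plain log-rank that the trial leaves confounding unaddressed; section 9.3 does not support this, and weighting held the error at 5% or below in every scenario.

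A reader might also infer that the trial is underpowered. It is not: the plain test exceeds 80% at the protocol's own effect. Gains of 4 to 9 points appear only if the true effect is 65–66% versus 40%, which the documents do not contain.

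It is tempting to say that age drives donor status, since siblings are typed only "if available and age < 70 years without cancer, thrombosis or cardiac failure history". But section 8.1 then turns to an 8/8 unrelated donor, and either type puts a patient in group A. Fewer usable siblings need not mean fewer donors, so confounding by age is possible, not shown.

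The medians in section 1.2 describe lower-risk patients generally. This trial requires a poor-prognosis feature, and section 1.4 expects median survival below 3 years, so the spread may be narrower and the gain nearer 2 to 3.5 points. Nor do the simulations test age, IPSS-R and comorbidity themselves, whose strength in patients without a donor is not given.

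Finally, covariates and strata can be left to an SAP, which is not at hand. For that reason the unnamed propensity covariates are not counted here. The protocol does, however, name the test and two main estimates, and leaves them unranked.

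**Conclusion.** The point holds in a limited form. The sizing test and first main estimate of a non-randomised trial use none of the prognostic factors that the protocol names and collects, and section 9.3 does not say whether that estimate or the weighted one decides.

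Size: about 2 to 6 power points at 70% versus 40% (7 in one scenario), on a test that already has about 86 to 92%. If imbalance favours donors, the plain test's error is roughly 7 to 24% against about 5% with adjustment. With a moderate score and a 0.2 SD imbalance there is hardly any rise. Every figure on gain and error rests on an assumed prognostic spread, and every figure on error also on an assumed imbalance. This is an improvement worth making, not a flaw that invalidates the trial.

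**What to change.** In section 9.3, define the direct comparison as a Cox model with donor group plus about three factors fixed in advance (age, IPSS-R category and comorbidity score at inclusion), or as a log-rank stratified by a short prognostic grouping. Donor type, although in the list in section 1.4, cannot be used because patients without a donor have none. Keep the propensity-weighted analysis, state which of the two decides, and report the plain log-rank and Kaplan-Meier curves as support. Either list the stratification parameters mentioned in section 8.1 or remove the phrase.

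Cost: wording only, no new data. The adjusted hazard ratio becomes conditional: in model A its median was 0.33 to 0.37 where the marginal one was 0.39, so it should not be read against the design value without saying so. With about 45 to 50 deaths the model should hold to about three covariates.
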